Clinical & laboratory investigations	
For Events of Deep Vein Thrombosis (DVT) within 15 days post-op.)
 
All of the patients underwent Routine bilateral compression Doppler.
 
For Clinical PE (Pulmonary Embolism) Events from Day of surgery and During Hospitalization period or end of study
 
Clinical PE events PE (Pulmonary Embolism) events were confirmed by spiral CT.
 
For follow up:
 
APTT should be done before the first dose then after 4 & 8 hours of the first dose, then on days 1,8,15 post operatively.

Study duration	
Enrolment period: 3 months duration
 
Follow-up duration: Follow-up per patient will be for a period of 15 days

Eligibility Criteria	
Inclusion Criteria:
 
 18 years of age or older Body Weight >60 kg Patients undergoing major orthopedic operations

	
Patients ready to sign informed consent form (ICF) Patients should discontinue any agents that affect haemostasis prior to the study medication use unless strictly indicated. These agents include medications such as: anticoagulants, thrombolytics, non-steroidal anti-inflammatory agents (including Ketorolac tromethamine), preparations containing aspirin, systemic salicylates, ticlopidine, dextran 40, clopidogrel, other anti-platelet agents including glycoprotein IIb/IIIa antagonists or systemic glucocorticoids.
 
Exclusion Criteria:
 
Significant bleeding injury such as solid organ laceration or intracranial bleed at discretion of attending physician Hypersensitivity to Hirudin or prior documented Allergy to its components Pregnant or breast feeding Hemorrhagic stroke in preceding 3 months abnormal baseline coagulation characterized by an INR >1.4, obtained at the discretion of the treating clinician Required therapeutic anticoagulation for atrial fibrillation, prior VTE, or mechanical heart valve Patients with a history of coagulation disorder Treatment with concomitant anti-platelet agent other than aspirin 326 mg or more daily (Platelet count < 100 X10⁹ /dl) Active bleeding Subjects with a life expectancy less than 1 month

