6.3. The Follow-up Phase

During this phase, which is approximately 15 days, PE which is confirmed by spiral CT chest, any new DVT appears also to be confirmed by Doppler ultrasound, Bleeding assessment, APTT will be done on days 1, 8 & 15, concomitant medications, Hospital stay and any adverse event data will all be recorded

7. FLOW CHARTS:

7.1. STUDY FLOW CHARTS:

Activity	Pre-operative phase (Screening)	Operative phase (Day 0)	Follow-up 1 (Day 1)	Follow-up 2 (Day 8)	Follow-up 3/ End of Study (Day 15)
ICF Signature	×				
Inclusion/Exclusion Criteria	×				
Demographic Data	×				
Medical History	×				
Vital signs	×				
Concomitant Medication	×				
Physical Examination	×				

Laboratory investigation	×		×	×	×
Type of surgery		×			
Assessment of bleeding		×	×	×	
IMP Administration		×	×	×	×
Assessment of DVT			×	×	×
Assessment of PE			×	×	×
Assessment of therapeutic response					×
APTT	×	×	×	×	×
Adverse Event		×	×	×	×
Study completion					×

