7.2. STUDY PHASES

The study consists of 3 phases:

Visit 1: Preoperative phase (screening)

- ❖ Patient Screening (Check eligibility)
- ❖ Signed ICF
- ❖ Gathering Patient Information as Demographic, Vital Signs, BMI, Physical Examination, Medical History, Concomitant medications
- ❖ Laboratory Investigations (Hb, PLt count, APTT, INR, SGPT, SGOT, Serum Albumin, Serum Bilirubin, serum creatinine, Creatinine clearance, Random blood sugar)
- ❖ Patients main complaint (Knee, Hip)

Operative phase (Day 0)

Patient Data to be collected:

- ❖ Type , Date of surgery
- ❖ Type of anaesthesia
- ❖ Patient position
- ❖ Type of prosthesis
- ❖ Blood transfusion

Start of IMP administration.

APTT 4 & 8 hours after IMP administration

Visit 2: Post operative phase (Follow-up 1 (Day 1))

- ❖ Assessment of bleeding
- ❖ Type of blood transfusions
- ❖ Assessment of DVT
- ❖ Routine bilateral compression Doppler (confirmation for DVT)
- ❖ Assessment of PE
- ❖ Spiral CT (confirming PE)
- ❖ IMP administration
- ❖ Laboratory investigations (Hb%, Platelets count)
- ❖ APTT

Assessment will be done in the hospital, as post-operative period before discharge from hospital.

Visit 3: Follow-up 2 (Day 8)

- ❖ Assessment of bleeding
- ❖ Type of blood transfusions
- ❖ Assessment of DVT
- ❖ Routine bilateral compression Doppler (confirmation for DVT)
- ❖ Assessment of PE
- ❖ Spiral CT (confirming PE)
- ❖ IMP administration
- ❖ Laboratory investigations (Hb%, Platelets count)
- ❖ APTT

Assessment in day 8 will be done from outpatient clinic in most patients.

Visit 4: Follow-up 3/ End of Study (Day 15)

- ❖ Assessment of bleeding
- ❖ Type of blood transfusions
- ❖ Assessment of DVT
- ❖ Laboratory Investigations
- ❖ Routine bilateral compression Doppler (confirmation for DVT)
- ❖ Assessment of PE
- ❖ Spiral CT (confirming PE)
- ❖ APTT
- ❖ End of Study

Assessment in day 15 will be done from outpatient clinic.

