8. STUDY OUTCOME MEASURES

8.1. Primary Endpoints

Primary end points included new onset symptomatic thrombosis requiring medical or surgical intervention or death due to thrombosis defined as fatal PE, ischemic

Sponsor: Minapharm Pharmaceuticals
Protocol Number: Sub-Thromb-001
Version: 1 amendment 1

stroke, mesenteric thrombosis, or myocardial infarction.

The number of clinical PE events will be measured by spiral CT

Mean changes in APTT where it will be done before first dose, 4 & 8 hours after first dose then on days 1,8,15 post operatively

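### Thrombotic death, including a fatal PE that was never imaged, is part of the primary endpoint but has no place in the primary analysis variables or in SAP Tables 8 and 9

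*Protocol*

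**What the plan says.** **Endpoint.** The synopsis, Protocol 8.1 and SAP 4.1 define the first primary endpoint as new symptomatic thrombosis that needs intervention, or "death due to thrombosis defined as fatal PE" or one of three other causes (myocardial infarction, ischemic stroke, mesenteric thrombosis). No imaging requirement is attached to the death component. A separate item in 8.1 and SAP 4.1 adds a PE count: "The number of clinical PE events will be measured by spiral CT".

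**Analysis variables.** Protocol 17.2.1 and SAP 8.2.1 list two primary variables: the proportion of patients with new symptomatic thrombosis, and the number of clinical PE events by spiral CT. Neither mentions death.

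**Tables.** SAP Table 8 carries the title of the first variable, but its rows record only whether a Doppler was done, who read it and what it showed. Table 9 does the same for spiral CT. Both have columns for Days 1, 8 and 15.

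**PE window.** The synopsis describes clinical PE events "from Day of surgery and During Hospitalization period or end of study". Protocol 6.3 has "During this phase, which is approximately 15 days, PE which is confirmed by spiral CT chest".

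**The concern.** In a prophylaxis trial, a fatal PE is the clearest failure of treatment, and the endpoint definition recognises this. The reported result, however, comes from the analysis variables and the table shells, and these accept a PE only with a CT report. A patient who dies before imaging has no such report. No section gives another route, such as autopsy or a rule for an unexplained death.

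The loss runs one way: leaving out a fatal event can only reduce the rate. With a single arm there is no control group in which the same loss would occur. The other thrombotic deaths named in the endpoint are affected too, because neither Table 8 nor Table 9 has a row for any of them.

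**Working it through.** **The plan's own figure.** The documents give no rate or precision for PE or thrombotic death. The only computed figure is the sample size of 168 (Protocol 17.1, SAP 8.1). It reproduces: 1.96² × 0.125 × 0.875 / 0.05² = 168.07. It concerns DVT and does not bear on this point.

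**Following one patient through the plan.** Take a patient who dies of PE on Day 5 with no CT.

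| Step | Place | Is the event counted? |
|---|---|---|
| Endpoint definition | Protocol 8.1, SAP 4.1 | Yes: fatal PE is named, with no CT condition |
| First primary variable | Protocol 17.2.1, SAP 8.2.1 | Death is not named |
| Second primary variable | Protocol 17.2.1, SAP 8.2.1 | No: PE is measured by CT |
| Table 8 | SAP 9.2 | No: Doppler rows only |
| Table 9 | SAP 9.2 | No: at most CT not done, with a reason |
| Table 13 | SAP 9.3 | Listed as a serious adverse event |
| Table 20 | SAP 9.4 | Listed as a discontinuation due to death |

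The event meets the endpoint in the first row and is in no primary event row after that.

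**Effect of one uncounted event.** Inputs: n = 100 (Protocol 17.1, and the N = 100 in the SAP tables) and 95% two-sided confidence. The event counts of 0 and 1 are assumed for illustration. Exact (Clopper-Pearson) limits:

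- 0/100: lower 0; upper = 1 − 0.025^(1/100) = 3.62%.
- 1/100: lower = 1 − 0.975^(1/100) = 0.03%; upper = 97.5th percentile of Beta(2, 99) = 5.45%.

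The estimate rises by 1 percentage point and the upper limit by 5.45 − 3.62 = 1.83 points, about half as much again (5.45 / 3.62 = 1.51).

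**How likely is at least one?** The documents give no rate of PE without CT, so this is an assumption shown over a range. The probability is 1 − (1 − r)^100:

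- r = 0.1%: 9.5%
- r = 0.5%: 39.4%
- r = 1%: 63.4%

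**PE window.** The synopsis phrase could mean the hospital stay or the whole study. Against it stand Protocol 6.3 (about 15 days), the flow chart in 7.1 (PE assessment at Days 1, 8 and 15), the visit lists in 7.2 (PE assessment and spiral CT at Days 8 and 15) and the Day 8 and Day 15 columns of SAP Table 9. All of these point to Day 15.

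**The case against.** The strongest reply is that Protocol 8.1 does not exclude the death. Fatal PE is part of the first endpoint without any CT condition, and the CT sentence belongs to a separate count. An analyst could treat the first analysis variable as shorthand for the full endpoint and count the death there. This stands as far as the endpoint wording goes. It does not settle the analysis, because Table 8, the shell for that variable, offers nothing but Doppler findings. Whether the death is counted would be decided after it is known.

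It is also true that the death would not vanish from the report, since Tables 13 and 20 would show it. But neither table feeds the primary result.

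A reader might infer more: that a PE after discharge is lost as well, because the synopsis mentions the hospitalization period and "Assessment in day 8 will be done from outpatient clinic in most patients". The documents do not support this. The synopsis phrase itself goes on to the end of the study, and the Day 8 sentence closes a visit list that includes PE assessment and spiral CT. It therefore shows PE being looked for in outpatients.

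Finally, the size is hypothetical. No PE or fatal PE rate is given, and nothing in the documents says how often such a death would go unimaged.

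**Conclusion.** The point holds as a mismatch between the endpoint and its analysis. Thrombotic death is a named primary event, yet the primary variables omit it and SAP Tables 8 and 9 have no row for it. Followed as written, the plan leaves a fatal PE without CT out of the primary result, and the omission can only make the rate look lower.

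One such event in 100 patients is the difference between 0% (0 to 3.62%) and 1% (0.03 to 5.45%). These figures rest on an assumed event count. The direction of the error does not.

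Two broader statements should be avoided. CT is the only route to the PE count and its table, not to the endpoint as defined in 8.1. On the window, what remains is loose synopsis wording, with no evidence of uncounted follow-up days.

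**What to change.** 1. In Protocol 17.2.1 and SAP 8.2.1, define the first primary variable as the proportion of patients with symptomatic thrombosis or death due to thrombosis up to Day 15.
2. In SAP Table 8, add rows for thrombotic death by cause: PE, ischemic stroke, mesenteric thrombosis, myocardial infarction.
3. For PE, in Protocol 8.1 and 17.2.1 and SAP 4.1 and 8.2.1, count CT-confirmed PE, PE found at autopsy if one is done, and deaths up to Day 15 in which PE cannot be excluded. In Table 9, report patients with PE as n/N with and without the last category.
4. Align the synopsis wording on the PE window with the Day 0 to Day 15 period already used in Protocol 6.3, 7.1 and 7.2 and SAP Table 9.

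**Cost.** Wording, some table rows, a CRF item for cause of death, and someone named to judge that cause. No imaging or visit is added. The downside is that some deaths in which PE cannot be excluded will have another cause; the paired rows show how much depends on them. Prespecified classification of cause of death is an alternative to the last category. The rule should be fixed before the data are seen.

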
Study objective
	
The primary objective of this study is to evaluate the efficacy of r-Hirudin RB variant 15 mg in DVT prophylaxis post major orthopedic operations
 
The secondary objective of this study is to evaluate the safety of r-Hirudin RB variant 15 mg in DVT prophylaxis post major orthopedic operations in terms of serious bleeding.

Study endpoint
	
Primary endpoint: Primary end points included new onset symptomatic thrombosis requiring medical or surgical intervention or death due to thrombosis defined as fatal PE, ischemic stroke, mesenteric thrombosis, or myocardial infarction.
 
Secondary endpoint: The Secondary end point of major bleeding is defined as clinically evident hemorrhage associated with a

	
hemoglobin decrease ≥ 2 g/dL that leads to a transfusion of ≥ 2 units of whole blood or packed red cells outside of the perioperative period (time from the start of the surgery or procedure and up to 12 hours after), or hemorrhage that is intracranial, retroperitoneal, or into a prosthetic joint. Recording serious adverse events (SAE)/ adverse events (AE) during the study duration.

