Statistical analysis	
- Descriptive analysis: All statistical tests used a significance level of P=0.05, two tailed tests are performed for all analyses used statistical testing. Descriptive analysis for quantitative data will include count, mean with 95% CI, standard deviation, median, minimum and maximum. For qualitative categorical variables; frequency and percentage and 95% confidence interval will be applied.

Stopping rules	
DVT PE Major bleeding Allergy APTT value increases by 2-2.5 folds According to investigator evaluation

Table of Contents

Title Page	1
1. Synopsis	2
Table of Contents	6
2. LIST OF ABBREVIATIONS	9
3. SIGNATURE(S) PAGE	10
4. INTRODUCTION	11
4.1. Background	11
4.2. Correlative studies:	11
4.3. Study Rationale	12
5. STUDY OBJECTIVES	12
5.1. Primary Objectives	12
5.2. Secondary objectives	12
6. TRIAL DESIGN	12
6.1. The pre-operative Phase	12
6.2. The operative Phase	13
6.3. The Follow-up Phase	13
7. FLOW CHARTS:	13
7.1. STUDY FLOW CHARTS:	13
7.2. STUDY PHASES	14
8. STUDY OUTCOME MEASURES	15
8.1. Primary Endpoints	15
8.2. Secondary Endpoints	16
9. STUDY POPULATION	16
9.1. Recruitment strategy:	16
9.2. Inclusion Criteria	16
9.3. Exclusion Criteria	16
10. STUDY PROCEDURE:	17
10.1. Selection of the study population:	17
10.2. Case Report Form	17
11. SOURCE DATA	17

12.	TREATMENT OF TRIAL PARTICIPANTS	18
12.1.	Description of Study Medication(s)	18
12.2.	Concomitant Medication (if applicable).....	19
13.	DATA COLLECTION	19
15.1.	DATA MANAGEMENT	20
15.2.	AMENDMENT TO THE PROTOCOL.....	20
15.2.1.	Protocol Deviations	20
15.2.2.	Onsite Audits.....	20
15.2.3.	Study Monitoring	21
15.3.	PREMATURE DISCONTINUATION OF STUDY.....	22
16.	SAFETY REPORTING AND DEFINITIONS	22
16.1.	Adverse Events Monitoring.....	22
16.2.	Reporting Period.....	23
16.3.	Adverse Event (AE):	23
16.4.	Serious Adverse Events	24
16.4.1.	Instructions for Reporting Serious Adverse Events	24
17.	STATISTICAL METHODOLOGY	24
17.1.	Determination of Sample Size.....	24
17.2.	Analysis Variables:.....	25
17.2.1.	Primary analysis variables:.....	25
17.2.2.	Secondary analysis variables:.....	25
17.2.3.	Statistical Method:.....	25
17.2.4.	Interim Analysis	25
18.	ETHICS.....	25
18.1.	INDEPENDENT ETHICS COMMITTEE (IEC) OR INSTITIUTIONAL REVIEW BOARD (IRB).....	25
18.2.	Ethical principles:	26
18.3.	Laws and regulations:	26
18.4.	PATIENT INFORMATION AND CONSENT	26
18.5.	DISCONTINUATION OF THE STUDY	27
18.5.1.	PREMATURE DISCONTINUATION OF STUDY	27

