17. STATISTICAL METHODOLOGY

17.1. Determination of Sample Size

Sample size: Records for 100 patients who underwent major orthopedic surgery collected from 1 site

The sample size is based on literature review for previous studies, and a sample of 168 patients will be sufficient to detect an incidence of 12.5% of DVT with an acceptable error of 5%, and a 95% confidence level

17.2. Analysis Variables:

17.2.1. Primary analysis variables:

Proportion of patients experienced new onset symptomatic thrombosis
The number of clinical PE (Pulmonary Embolism) events will be measured by spiral CT

17.2.2. Secondary analysis variables:

Number of adverse events recorded
Proportion of patients experienced major bleeding

17.2.3. Statistical Method:

Descriptive analysis:

All statistical tests used a significance level of $P=0.05$, two tailed tests were performed for all analyses used statistical testing.

Descriptive analysis for quantitative data will include count, mean with 95% CI, standard deviation, median, minimum and maximum. For qualitative categorical variables; frequency and percentage and 95% confidence interval will be applied.

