8.2 Analyses variables

8.2.1 Primary analysis variables:

- Proportion of patients experienced new onset symptomatic thrombosis
- The number of clinical PE (Pulmonary Embolism) events will be measured by spiral CT

8.2.2 Secondary analysis variables:

- Number of adverse events recorded
- Proportion of patients experienced major bleeding

8.2.3 Statistical Method:

Descriptive analysis:

All statistical tests used a significance level of $P=0.05$, two tailed tests were performed for all analyses used statistical testing.

Descriptive analysis for quantitative data will include count, mean with 95% CI, standard deviation, median, minimum and maximum. For qualitative categorical variables; frequency and percentage and 95% confidence interval will be applied.

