9.2 Primary End Point

Table 8 *Proportion of patients experienced new onset symptomatic thrombosis*

		Follow-up 1 (Day 1)	Follow-up 2 (Day 8)	Follow-up 3/ End of Study (Day 15)	p-value
Was a Routine bilateral compression Doppler done?	Yes, N (%)				
	No, N (%)				
If “No”, please indicate a reason	Reason 1, N (%)				
	Reason 2, N (%)				
	Reason 3, N (%)				
Is the report interpreted, signed & dated by the PI or any of the designated site staff?	(Yes), N (%)				
	(No), N (%)				
If “No”, please indicate a reason:	Reason 1, N (%)				
	Reason 2, N (%)				
	Reason 3, N (%)				
If “Yes”, the report interpretation shows that the subject is:	Normal, N (%)				
	Abnormal, N (%)				
If abnormal, please state the reason:	Reason 1, N (%)				
	Reason 2, N (%)				
	Reason 3, N (%)				

Table 9 *The number of clinical PE (Pulmonary Embolism) events will be measured by spiral CT*

		Follow-up 1 (Day 1)	Follow-up 2 (Day 8)	Follow-up 3/ End of Study (Day 15)	p-value
Was a Spiral CT done?	Yes, N (%)				
	No, N (%)				
If “No”, please indicate a reason	Reason 1, N (%)				
	Reason 2, N (%)				
	Reason 3, N (%)				
Is the report interpreted, signed & dated by the PI or any of the designated site staff?	(Yes), N (%)				
	(No), N (%)				
If “No”, please indicate a reason:	Reason 1, N (%)				
	Reason 2, N (%)				
	Reason 3, N (%)				
If “Yes”, the report interpretation shows that the subject is:	Normal, N (%)				
	Abnormal, N (%)				
If abnormal, please state the reason:	Reason 1, N (%)				
	Reason 2, N (%)				
	Reason 3, N (%)				

Table 10 *Mean changes in Activated Partial Thromboplastin Time (APTT) where it will be done before first dose, 4 & 8 hours after first dose then on days 1,8,15 post operatively*

		Before 1 st dose	After 1 st dose		Post-operative			p- value
			4 h	8 h	Day 1	Day 8	Day 15	
Was an APTT test performed?	Yes, N (%)							
	No, N (%)							
If “No”, please indicate a reason	Reason 1, N (%)							
	Reason 2, N (%)							
	Reason 3, N (%)							
If “Yes”, the test result is	APTT; Mean ± SD (sec)							
APTT, % change								
p-value								
The test interpretation shows that the subject is:	Normal, N (%)							
	Abnormal, N (%)							
If abnormal, please state the reason:	Reason 1, N (%)							
	Reason 2, N (%)							
	Reason 3, N (%)							

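### Mean APTT change is primary in some sections and absent from others, so a clotting-test result could be reported as primary efficacy for DVT prophylaxis

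*Protocol*

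**What the plan says.** Three places treat APTT as primary. Protocol 8.1 ends its list of primary endpoints with "Mean changes in APTT where it will be done before first dose", then 4 and 8 hours after that dose and on days 1, 8 and 15. SAP 4.1 carries the same item. In SAP 9.2, headed as the primary endpoint results, Table 10 is titled "Mean changes in Activated Partial Thromboplastin Time (APTT) where it will be done before first dose" and so on, with columns for six time points, a percentage-change row, and both a row and a column for p-values.

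Three places do not. Protocol 17.2.1 names two primary analysis variables: "Proportion of patients experienced new onset symptomatic thrombosis" and the count of clinical PE events. SAP 8.2.1 names the same two, the second being "The number of clinical PE (Pulmonary Embolism) events will be measured by spiral CT". The synopsis endpoint row is narrower still: "Primary end points included new onset symptomatic thrombosis requiring medical or surgical intervention or death due to thrombosis defined as fatal PE", followed by the other fatal thrombotic events.

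Elsewhere APTT has a different role. The synopsis lists it under follow-up: "APTT should be done before the first dose then after 4 & 8 hours of the first dose". The synopsis stopping rules include "APTT value increases by 2-2.5 folds", and Protocol 15.3 and 18.5.1 give a rise of that size as a ground for terminating the trial. The primary objective in the synopsis, Protocol 5.1 and SAP 3.1 is efficacy in DVT prophylaxis.

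**The concern.** Both documents disagree with themselves about what is primary, and the item in dispute is a laboratory measure of drug activity. The protocol's background section describes the drug as a direct thrombin inhibitor that blocks coagulation, so some movement in a clotting time is to be expected from its mechanism. Such movement says the drug is active. It does not say that thrombosis was prevented, which is the objective.

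In a single-arm trial this matters more than usual. The documents give no reference rate against which the thrombosis proportion could be tested. A before-after APTT comparison, by contrast, produces a p-value without any comparator, and SAP 9.2 sets out cells for one. At stake is whether the report could present a significant APTT change under the primary endpoint heading as evidence of prophylactic efficacy.

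**Working it through.** **Step 1: set the passages side by side.**

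| Place | Thrombosis | PE events as a separate item | Mean APTT change |
|---|---|---|---|
| Synopsis, primary endpoint | yes | no (fatal PE is within the endpoint) | no |
| Protocol 8.1 | yes | yes | yes |
| Protocol 17.2.1 | yes | yes | no |
| SAP 4.1 | yes | yes | yes |
| SAP 8.2.1 | yes | yes | no |
| SAP 9.2, Tables 8 to 10 | yes | yes | yes, with p-values |

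APTT is also missing from every secondary list: the synopsis secondary row, Protocol 8.2 and 17.2.2, and SAP 4.2 and 8.2.2 cover only major bleeding and adverse events. It is therefore either primary or has no endpoint status, depending on the section read.

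**Step 2: look for a rule that settles its role.** Protocol 17.2.3 and SAP 8.2.3 set a two-sided 0.05 level and describe summary statistics. Neither names a test for Table 10, states which direction of APTT change is favourable, orders the primary endpoints, or says what result would count as success.

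**Step 3: look at what the change measures.** Protocol 6.1 and the flow chart place the baseline APTT in the pre-operative phase. Protocol 6.2 starts dosing about six hours after the operation, or once haemostasis allows, with APTT 4 and 8 hours after that dose. For patients dosed on that schedule, the operation lies between the baseline sample and every later one. The paired change may therefore reflect surgery as well as the drug.

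**Step 4: how easily would it be significant?** The plan gives no figure for APTT to reproduce. Its only sample-size calculation is for DVT incidence: 1.96² × 0.125 × 0.875 / 0.05² = 168.06, which agrees with the stated 168 and contains no APTT term.

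Inputs: N = 100 (Protocol 17.1) and two-sided alpha 0.05 (Protocol 17.2.3). The documents give neither an APTT standard deviation nor an expected change. The effect is therefore an assumption, expressed as d = mean change divided by the SD of the within-patient differences, with all 100 pairs complete.

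Change detectable with 80% power, normal approximation: d = (1.960 + 0.842) / √100 = 0.280.

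Power of the paired t-test (noncentral t, 99 degrees of freedom, noncentrality d × √100):

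| Assumed d | Power |
|---|---|
| 0.1 | 17% |
| 0.2 | 51% |
| 0.28 | 79% |
| 0.3 | 84% |
| 0.5 | 99.9% |

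A shift of half a within-patient SD would almost always be significant, whatever happened to thrombosis. A shift of 0.1 to 0.2 SD would not be reliably detected.

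**The case against.** The strongest reply is that nothing in the plan makes APTT decisive. The only method section is headed as descriptive, the objective is DVT prophylaxis, and no result is defined as success. That stands, and it limits the point to what could be reported. A reader might infer that the trial is set up to be declared positive on APTT; the documents do not say so, though they do not rule it out either.

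A reader might also infer that a larger APTT rise counts both as a treatment response and as a reason to stop. The documents never call an APTT rise a response or say that more is better. A group mean change and an individual limit can coexist. What remains is that the role of APTT is undefined.

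Nor does being paired make APTT the one clean p-value in the plan. Its baseline precedes surgery, and Tables 8 and 9 have p-value columns too, although comparing visits does not test prophylactic efficacy.

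It is tempting to add a familywise error rate for the five post-baseline APTT columns. The SAP does not say that five separate tests will be run, and such contrasts would share patients and a baseline, so a figure that assumes independence is not supported. The precision of the thrombosis proportion at 100 patients is a separate question about sample size.

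Finally, the conflict over PE is weaker than that over APTT. Fatal PE is already in the synopsis endpoint, and symptomatic PE can be read as symptomatic thrombosis.

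**Conclusion.** The inconsistency is certain: Protocol 8.1, SAP 4.1 and SAP 9.2 treat mean APTT change as primary, while Protocol 17.2.1, SAP 8.2.1 and the synopsis do not. The consequence is a possibility, not a stated intention. Because no success criterion, direction or test is given, a significant APTT change could be presented as a primary efficacy result although it does not measure prevention of DVT and may partly reflect surgery.

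The size depends on an assumed effect. With 100 complete pairs at two-sided 0.05, about 0.28 SD of the within-patient differences gives 80% power and 0.5 SD gives over 99%. Whether the true change is that large cannot be judged from the documents. The inconsistency should be corrected before analysis; the need to do so does not depend on the power figures.

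**What to change.** - Remove mean APTT change from the primary endpoints in Protocol 8.1 and SAP 4.1.
- List it as a secondary pharmacodynamic/safety measure in Protocol 8.2 and 17.2.2, SAP 4.2 and 8.2.2, and the synopsis secondary row. Changing only the endpoint sections would recreate the mismatch among the secondary lists.
- Move Table 10 from SAP 9.2 to 9.3. If its p-values are kept, name the test.
- Word the primary thrombosis endpoint identically in the synopsis, Protocol 8.1 and 17.2.1, and SAP 4.1 and 8.2.1, and state there whether PE is a component of it or a separate endpoint.
- Reconcile the passages that use APTT as a stopping criterion (synopsis stopping rules, Protocol 15.3 and 18.5.1) with its endpoint role. This is for the sponsor and the investigator to settle.

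The cost is rewording and moving one table. APTT loses its primary status. Every visit, sample and measurement stays as planned, and the sample-size basis is untouched because it does not use APTT.
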